5.2.3 Secondary Outcomes Analyses

We will analyze all-cause mortality with a Cox proportional hazards model, re-operation for disease relapse and other indications with frailty models to account for recurrence, and patient-reported outcomes using linear regression models.

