4.4 Randomization

After providing informed consent, participants will be randomized in a 1:1 ratio to receive either resection and reconstruction or internal fixation. A centralized web-based randomization system (www.randomize.net) will be used to ensure the concealed allocation of participants. Treatment allocation will be determined using random variable block sizes to avoid a substantial imbalance in the number of participants assigned to each treatment group. To ensure balance across groups for any key prognostic and treatment-related variables, such as regional differences in MBD management, the randomization process will be stratified by: 1) impending or pathologic fracture, and 2) clinical site.

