4.6 Data Collection and Participant Follow-Up

At baseline, we will collect pre-operative demographic and cancer-related data from various sources, including the participant or proxy, the participant's medical chart, and/or the participant's treating surgeon. The data will include details such as age, sex and gender, co-morbidities, life-expectancy based on surgeon estimate and pre-surgical functional status, and anatomic characteristics of the femoral metastatic lesion. Participants will also pre-operatively complete the PROM questionnaires. We will document surgical details, peri-operative care, and in-hospital data, including the timing of surgery and any co-interventions used that may mediate treatment effects (such as post-operative mobilization and therapy), as well as any serious adverse events (SAEs) that occurred during hospitalization. After discharge, participants will be followed for one year, during which they will be assessed by their treating surgeon at two and six weeks; four, six and nine months; and one-year post-surgery. At each visit, we will document physical therapy, ability to ambulate, re-operations, hospitalizations, and SAEs. PROM data will be collected at all visits; however, the burden is low due to the short nature of the questionnaire. The utility score from the PROPr: PROMIS®-Preference Scoring System will be collected at baseline and 6 and 12 months. Trial data will be securely stored in the trial database accessible only to authorized personnel. See **Table 4** below:

Table 4. Study Flow

CATEGORY	STEPS		DATA COLLECTED
Recruitment	Identification of Patients		
	Assessment of Patient Eligibility		Screening Data
	Informed Consent		Informed Consent Form
Pre-Operative (Baseline)	Pre-Operative (Baseline)		Demographics Cancer-related data PROMIS®-PROPr questionnaire PROMIS® Physical Function
	RANDOMIZATION 		
Follow Up Visits	Internal Fixation	Resection and Reconstruction	
	Peri-Operative	Peri-Operative	Surgical details Peri-operative care Serious Adverse Events (SAEs)
	2 Week	2 Week	Follow-Up Data Package: X-rays; PROMIS® Physical Function questionnaire; Demographics, health-related questions, Mortality Status; Patient-reported days at home; Recurrence of cancer; SAEs
	6 Week	6 Week	Follow-Up Data Package: X-rays; PROMIS® Physical Function questionnaire; Demographics, health-related questions, Mortality Status; Patient-reported days at home; Recurrence of cancer; SAEs

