5.0 Statistical Plan

5.1 Sample Size Determination

The use of hierarchically assessed composite outcomes is becoming more frequent in clinical trials, and it offers several benefits. By utilizing a pre-defined rank, statistical power increases while avoiding concerns of increased type I errors due to multiplicity. This ranked approach also aligns with clinical practice as patients and care providers are typically interested in the treatment effect on multiple outcomes with a defined hierarchy. Detailed simulations were performed to determine the appropriate sample size to adequately power the study. **Table 5** lists the distributional assumptions for each component of the composite outcome by treatment arm. Using 10,000 simulations of these distributions, we determined that 300 patients (150 per group) provided over 90% power to detect superiority with a two-sided alpha of 5% tested with the U-statistic described by Bebu and Lachin²⁶. To account for up to 10% attrition, the trial plans to enroll 334 patients.

Table 5 : Input for sample size estimation.

Rank	Outcome	Resection and Reconstruction	Internal Fixation
1	Death within 12 months	30%	30%
2	Physical function (ability to perform everyday activities) by 4 months		
	Unable to do	5%	10%
	With much difficulty	20%	25%
	With some difficulty	40%	40%
	With little difficult	25%	20%
	Without any difficulty	10%	5%
3	Days at home within 365 days, mean (SD)	340 (20)	300 (20)

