5.2 Statistical Methods

5.2.1 Analysis Plan Overview

While conducting the analyses, the data analysts will remain blinded to treatment allocation. The analysis and reporting of the trial will follow the CONSORT criteria (www.consort-statement.org). The process of participant enrolment and flow through the study will be summarized using a flow diagram. Participant demographics and baseline outcome variables will be summarized using descriptive statistics reported as mean (standard deviation) or median (interquartile range) for continuous variables depending on the distribution, and count (percent) for categorical variables. All analyses will use the intention-to-treat principle. We do not plan to conduct a formal interim analysis for efficacy, as the trial will not be stopped early for benefit due to the risk of overestimating treatment effects. Secondary analyses will be exploratory with no adjustments for multiple comparisons.

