5.2.2 Primary Outcome Analysis

We will hierarchically assess the primary composite outcome using the Win Ratio method. The Win Ratio method is based on the principle that each participant in the clinical trial is compared with every other participant within each stratum in a pairwise manner. All-cause mortality comparisons will be time-to-event and local cancer recurrence will allow for recurrent events using a frailty model. The pairwise comparison proceeds in a hierachal fashion – for example, starting with mortality, followed by physical function, followed by days at home, and finally by local cancer recurrence when participants cannot be differentiated on an outcome of higher importance. If two paired participants both experienced a local cancer recurrence, we will assume a greater frequency of recurrences to be worse. If two paired participants have the same mortality status or frequency of recurrences, we will assume earlier events are worse. For each pairwise comparison, the treatment groups are assigned a

win, loss, or tie. The Win Ratio is the frequency of a favorable outcome in participants assigned to resection and reconstruction divided by the frequency of a favorable outcome in participants assigned to internal fixation with a 95% CI and corresponding p-value calculated using the methods described by Finkelstein and Schoenfeld.

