5.2.5 Sensitivity Analyses

Assessment of the sensitivity or robustness of the findings to the key assumptions is essential in clinical trials. The following sensitivity analyses will be performed:

- 1) Baseline Prognostic Imbalance Analysis: This analysis will assume a baseline prognostic imbalance between the treatment groups. Adjusted analyses, employing Cox regression models, will be utilized to examine and control for the possible influence of patient factors that might be associated with the elements of the hierachal composite outcome.
- 2) “As-Treated” Analysis: This sensitivity analysis will account for crossovers in the surgical intervention. The actual surgical intervention will be the independent variable.

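### The mortality Cox model has no stated terms and adjustment is left to an imbalance-based sensitivity analysis; if mortality truly differs, omitting baseline life expectancy costs some power

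*Protocol*

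**What the plan says.** For mortality as a separate endpoint, Protocol 5.2.3 (Secondary Outcomes Analyses) says "We will analyze all-cause mortality with a Cox proportional hazards model". It lists no model terms, for this outcome or for the others in the same sentence.

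Adjustment appears in 5.2.5, as the first sensitivity analysis: "Adjusted analyses, employing Cox regression models, will be utilized to examine and control for the possible influence of patient factors". Its stated premise is that the arms differ in baseline prognosis. The factors are not named.

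Four other places bear on the point:

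- Section 4.4: "the randomization process will be stratified by: 1) impending or pathologic fracture, and 2) clinical site".
- Section 4.6: baseline data include "life-expectancy based on surgeon estimate and pre-surgical functional status". The study-flow table places baseline collection before randomisation, and 5.2.3 (Subgroup Analyses) already splits life expectancy at one year.
- Section 5.2.2: in the primary win ratio, where mortality ranks first, "each participant in the clinical trial is compared with every other participant within each stratum". The strata are not defined there.
- Section 5.2.1: "Secondary analyses will be exploratory with no adjustments for multiple comparisons".

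**The concern.** The order of the analyses suggests that prognostic covariates matter only if randomisation happens to leave the arms unbalanced. In a Cox model that is incomplete. The hazard ratio is non-collapsible: when a real treatment effect exists and a strong predictor of death is left out, the model estimates a marginal hazard ratio nearer 1 than the conditional one, even with perfect balance. The test also loses some power.

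The protocol expects equal mortality, so one natural use of this analysis is to see whether the more invasive operation is associated with more deaths. Deaths will be few, which makes an avoidable loss of information worth removing. In addition, because 5.2.5 names no covariates, nothing in the protocol fixes which adjusted model will stand beside the main one, or which hazard ratio leads if the two differ.

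**Working it through.** **The plan's own figures.** Section 5.1 needs 300 participants and allows 10% attrition: 300 / (1 − 0.10) = 333.3, rounded up to 334, as stated. The power of over 90% belongs to the composite. No hazard ratio, number of deaths or power is given for the mortality model. Table 5 gives "Death within 12 months" as 30% in each arm, so the expected deaths are 0.30 × 334 = 100.2.

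**What that number of deaths can show.** Schoenfeld's formula for 1:1 allocation is power = Φ(|ln HR| × √D / 2 − 1.96). It uses the "two-sided alpha of 5" per cent that 5.1 sets for the composite. With D = 100.2 and HR 1.5: 0.405 × 10.01 / 2 − 1.96 = 0.07, so power is 53%. The same formula gives 20% at HR 1.25, 80% at 1.75 and 93% at 2.0.

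**Effect of omitting the predictors, true HR 1.5.** There were 5,000 simulated trials per row, with 334 participants and 30% one-year mortality in the control arm (both from the protocol), and allocation balanced within fracture status. The following are assumptions, not protocol figures: exponential survival, 40% realised fracture, 50% with shorter life expectancy, the treatment hazard ratio and the predictor hazard ratios. Each cell gives the average HR and the power.

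| Predictor HR: fracture / life expectancy | Unadjusted | Stratified by fracture only | Adjusted for both | Power gain, adjusted − unadjusted |
|---|---|---|---|---|
| 1.2 / 1.5 | 1.50, 59.3% | 1.50, 59.4% | 1.51, 60.5% | 1.2 points |
| 1.5 / 2.0 | 1.48, 55.9% | 1.49, 56.3% | 1.50, 58.8% | 2.9 points |
| 1.5 / 3.0 | 1.47, 53.9% | 1.47, 54.2% | 1.51, 59.5% | 5.6 points |
| 2.0 / 4.0 | 1.44, 49.3% | 1.45, 50.8% | 1.51, 57.8% | 8.5 points |

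These powers can exceed the Schoenfeld 53% because the excess hazard raises the deaths to about 117 to 119. Simulation error is about √(0.55 × 0.45 / 5,000) = 0.7 points per power figure, and less for differences within a row. Stratifying by fracture alone adds at most 1.5 points and 0.01 on the hazard ratio; the rest comes from life expectancy.

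**True HR 1.7, with the model proposed below** (stratified by fracture, life expectancy as covariate). There were 2,000 trials per row, with 40% realised fracture and 40% with life expectancy under one year, both assumed.

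| Predictor HR: life expectancy / fracture | Unadjusted | Proposed model | Power gain |
|---|---|---|---|
| 2 / 1.3 | 1.68, 81% | 1.70, 83% | 2 points |
| 3 / 1.5 | 1.64, 76% | 1.71, 83% | 7 points |
| 5 / 1.5 | 1.59, 71% | 1.71, 84% | 13 points |

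**True HR 1, the protocol's own assumption.** In every setting tried, all models average about 1.00 and reject in about 4 to 5% of trials.

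**Scale of the assumed effects.** Ignoring strata, HR 1.5 on 30% control mortality implies 1 − 0.7^1.5 = 41% deaths, and HR 1.7 implies 1 − 0.7^1.7 = 45%. Both are large excesses that the protocol does not anticipate.

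**The case against.** The strongest reply is that the defect is read from silence. Section 5.2.3 names model families only, never says unadjusted or unstratified, and the terms of a secondary model are commonly left to a statistical analysis plan, which is not at hand. For stratification this stands: a reader might infer that the protocol rules out stratifying by fracture status, but it does not say so, and the primary analysis does compare within strata. For prognostic covariates it stands only in part. Making the adjusted Cox model a sensitivity analysis implies that the main model lacks those covariates, and the stated reason is imbalance alone.

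A reader might also infer that the planned hazard ratio is biased toward 1. That is too strong. Under randomisation the unadjusted ratio is a valid marginal quantity, different from the conditional one. Nor does it shrink when mortality is equal.

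A further tempting inference is that excess deaths would go unnoticed. The documents do not support it. Sites report all serious adverse events, including fatal ones, and the DSMB reviews them. Nothing states that this Cox model is the safety check. The endpoint is exploratory, and its main limit is about 100 expected deaths, which adjustment does not change.

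Finally, predictor strength is unknown. Life expectancy here is a surgeon's judgement in a population already restricted to at least six months, so the weaker rows may be the realistic ones. This stands, and it is why the size is given as a range.

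**Conclusion.** The point holds in a limited form. As written, the protocol points to a main mortality model without prognostic covariates and treats adjustment only as a remedy for imbalance, with the covariates unnamed. If mortality truly differs, that choice costs about 1 to 9 points of power at a hazard ratio of 1.5 and about 2 to 13 points at 1.7. The upper ends require strong predictors: hazard ratios for life expectancy of 4 and 5 respectively. At 1.5 the average unadjusted hazard ratio is 1.44 to 1.50. If mortality is equal there is no effect. The treatment effect, predictor strengths, prevalences and survival shape are all assumed, because the protocol gives none of them. This is an inexpensive improvement to an exploratory analysis and leaves the primary result untouched.

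**What to change.** In 5.2.3 (Secondary Outcomes Analyses), define the main mortality analysis as a Cox model stratified by fracture status and adjusted for the surgeon's baseline life-expectancy estimate, coded under one year versus one year or more as in the subgroup analysis. State that it is used whether or not imbalance is seen, that it remains exploratory, and that the unadjusted hazard ratio is reported as supportive.

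State also how clinical site, the other randomisation stratifier, is handled. Full stratification by both factors would be sparse: 20 to 30 sites × 2 fracture groups gives 40 to 60 strata, or about 100 / 60 = 1.7 to 100 / 40 = 2.5 deaths each. If the analysis in 5.2.5 is kept, name its covariates.

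The cost is a few sentences, since the variables are already collected. The downsides are that the leading hazard ratio becomes conditional on these variables, and that missing life-expectancy estimates need a rule set in advance.

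### The linear regression for the patient-reported secondary outcomes names neither the baseline score nor the randomisation stratum as a covariate, and the only adjusted analysis is a Cox model that does not fit a score

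*Protocol*

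**What the plan says.** Section 5.2.3 (Secondary Outcomes Analyses) is one sentence that assigns a model family to each type of outcome. Its whole provision for function and the PROPr utility is "patient-reported outcomes using linear regression models". It names no covariate for any model.

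The baseline values exist. Section 4.6 states: "Participants will also pre-operatively complete the PROM questionnaires". It adds that the PROPr utility score "will be collected at baseline and 6 and 12 months", and the study flow table lists both instruments at the pre-operative visit. The only use the protocol states for baseline outcome values is descriptive: "Participant demographics and baseline outcome variables will be summarized using descriptive statistics" (Section 5.2.1).

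Under Section 4.4, "the randomization process will be stratified by: 1) impending or pathologic fracture, and 2) clinical site". The primary win ratio takes account of strata, because Section 5.2.2 makes its pairwise comparisons within each stratum. Nothing equivalent is said for the linear models.

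Section 5.2.5 holds the only covariate-adjusted analysis, a sensitivity analysis for baseline imbalance: "Adjusted analyses, employing Cox regression models, will be utilized to examine and control for the possible influence of patient factors". The factors in question are those associated with elements of the composite, and function is one of those elements.

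Section 5.2.1 sets the status of these analyses: "Secondary analyses will be exploratory with no adjustments for multiple comparisons".

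**The concern.** Read together, Sections 5.2.1, 5.2.3 and 5.2.5 point towards an unadjusted main comparison of function and PROPr. The one adjusted analysis uses a model for event times, whereas function is a 1-5 item and PROPr is a utility score. As written, there is no adjusted analysis that could be applied to either.

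Two things are at stake. First, precision: a score measured before surgery usually explains part of the same score afterwards, and leaving it out gives that up. Second, a chance difference in baseline function between the arms stays in the unadjusted estimate.

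Function at 4 months is level 2 of the composite and also a separate secondary endpoint, and PROPr is described as a further key secondary outcome. Table 5 assumes equal mortality in the two arms, so the separate function result will matter when a win on the composite is interpreted. Naming the covariates in advance also removes a later choice between adjusted and unadjusted results.

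**Working it through.** **The plan's own figure.** Section 5.1 gives 300 evaluable patients (150 per group), over 90% power and 334 enrolled after 10% attrition. The enrolment figure reproduces: 300 / 0.9 = 333.3, rounded up to 334. Simulating the Table 5 hierarchy at 150 per arm, with death as a yes/no outcome and the Bebu-Lachin variance (2,000 runs), gives 91% power. These figures concern the primary outcome only. The protocol states no power, standard deviation (SD) or correlation for a linear model of any patient-reported secondary outcome.

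**Inputs from the protocol.** Table 5 gives the 4-month function distribution, worst to best category, as 5/20/40/25/10% for resection and 10/25/40/20/5% for fixation. Twelve-month mortality is 30% in each arm. Table 2 shows different expected function values; Table 5 is used here because it is the sample size input.

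**Assumptions not in the protocol.** The five categories are scored 1-5. The hazard of death is constant over the year. The baseline to follow-up correlation, rho, is 0.3-0.6, with 0-0.7 shown as a wider range.

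**Means and SD.**
- Resection mean: 1(0.05) + 2(0.20) + 3(0.40) + 4(0.25) + 5(0.10) = 3.15
- Fixation mean: 1(0.10) + 2(0.25) + 3(0.40) + 4(0.20) + 5(0.05) = 2.85
- Difference: 0.30
- Variance, resection: 10.95 - 3.15² = 1.0275. Variance, fixation: 9.15 - 2.85² = 1.0275. SD = 1.014 in each arm.

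**Patients with a 4-month score.** Alive at 4 months: 150 × 0.7^(1/3) = 133 per arm.

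**Effect of adjustment.** Residual variance with the baseline score in the model is (1 - rho²) times the unadjusted variance. The equivalent gain in sample size is 1/(1 - rho²) - 1.

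| rho | Reduction in residual variance | Equivalent extra patients |
|---|---|---|
| 0 | 0% | 0% |
| 0.2 | 4% | 4% |
| 0.3 | 9% | 10% |
| 0.4 | 16% | 19% |
| 0.5 | 25% | 33% |
| 0.6 | 36% | 56% |
| 0.7 | 49% | 96% |

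**Power for 4-month function, two-sided 5%, normal approximation.**
- Unadjusted standard error (SE) = 1.014 × √(2/133) = 0.124.
- Unadjusted: 0.30/0.1243 = 2.41; 2.41 - 1.96 = 0.45; power about 67%.
- Adjusted: the SE is multiplied by √(1 - rho²).

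| Per arm | Unadjusted | rho 0.3 | rho 0.4 | rho 0.5 | rho 0.6 |
|---|---|---|---|---|---|
| 133 (constant hazard) | 67% | 72% | 75% | 80% | 85% |
| 150 (no deaths by 4 months) | 73% | 77% | – | 84% | 89% |
| 105 (all 12-month deaths before 4 months) | 57% | 61% | – | 70% | 76% |

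The last two rows bracket the survival assumption. The table counts only the baseline score. No matching calculation is possible for PROPr, because the protocol gives no expected values for it.

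**The case against.** The strongest objection is that Section 5.2.3 is silent rather than wrong. It names model families, not covariates, and linear regression is exactly the framework that carries a baseline covariate. The covariate list of a secondary model is commonly left to the SAP, which is not shown. A reader might infer that the protocol excludes the baseline score; the text does not support that, since the score is neither named nor ruled out. This part stands. What remains is that the protocol does not leave adjustment wholly open: it places it in a sensitivity analysis and names a model that cannot be used for function or PROPr.

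The second objection is that the size depends on an unstated correlation. This also stands. With impending and realised fractures mixed, pre-operative function could predict 4-month function poorly (again an assumption), and the gain could be near zero. The 9-36% is an illustration, not a property of this trial.

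Third, the consequence is limited. The analyses are exploratory and the protocol claims no power for them, so 67% breaches no target. A reader might infer that the unadjusted comparison is biased. It is not: randomisation protects it, deaths and missing data aside, and only precision and chance imbalance are affected. Nor does the point reach the primary analysis or the sample size. Function is part of the composite, but Section 5.2.3 does not govern the win ratio, which already works within strata.

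Finally, adjusting for fracture status but not for site, the other stratification factor, needs a reason. With 334 patients over 20-30 sites, there are only about 11-17 per site (334/30 to 334/20). How to handle so many small strata is a separate choice that the SAP can make.

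**Conclusion.** The point holds as a low-severity improvement. The protocol does not specify the baseline score or the randomisation stratum in the linear models for patient-reported outcomes, and the adjusted analysis it does specify does not fit those outcomes. If the models are run without the baseline score, the residual variance is larger than it need be. The avoidable part is rho²: 9-36% for an assumed rho of 0.3-0.6, or 0-49% for 0-0.7. For 4-month function, that is a rise in power from about 67% to 72-85%, given Table 5, scoring of 1-5, a constant hazard and the assumed rho. If the unseen SAP already names these covariates, only the Cox wording in Section 5.2.5 remains to be corrected.

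**What to change.** In Section 5.2.3 (Secondary Outcomes Analyses), state that function at 4 months and PROPr at 6 and 12 months will be analysed by linear regression with treatment, the baseline value of the same score and fracture status as covariates. In Section 5.2.5, name a linear model instead of Cox regression for the adjusted analysis of function. The treatment of clinical site can be settled in the SAP.

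The cost is a few words in the protocol or SAP. The baseline scores and fracture status are already collected, and neither the sample size nor the primary analysis changes.
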